#### 3.0. Research Plan:

#### 3.1. Purpose:

This will be a prospective, double-blinded, randomized controlled trial on a convenience sample of patients presenting to the Emergency Department (ED) with a chief complaint of headache.

#### 3.2. Hypotheses, Research Questions or Objectives:

We will determine the difference in pain scores between the compazine and Ketamine groups, as measured by a 25-mm difference between the groups mean on the visual analogue scale (VAS) at 60 min.

#### 4. Brief Summary of the study:

We are comparing Ketamine to compazine for benign headaches in the ED. Subjects will be randomized into 1 of 2 groups. Group 1 will receive standard treatment of compazine 10 mg IV along with diphenhydramine (Benadryl) 25 mg IV. Group 2 (research arm) will receive Ketamine 0.3 mg/kg along with ondansetron (Zofran) 4 mg IV. Subjects will be seen at 15, 30, 45, and 60 minutes post-intervention to obtain Heart Rate, Blood Pressure, Headache severity, Nausea severity, Vomiting severity, Anxiety severity, and Restlessness severity. At 24-48 hours post intervention we will contact subjects and assess their pain and assess their satisfaction with their migraine pain management as part of this study. Subjects' participation will last up to 48 hours post headache. Diphenhydramine (Benadryl) and Ondansetron (Zofran) are being given in this study to manage the side effects from the comparison medications (Compazine –akathisia, ketamine –nausea). Diphenhydramine (Benadryl) itself doesn't add any benefit for migraines. [21] Ondansetron (Zofran) significantly reduces ketamine associated emesis [22]. Since nausea is common in migraines (73%) [23], and ketamine does not itself correct this it's logical and ethical to add this as an adjunct for ketamine. If we didn't add it to the regiment our satisfaction data would likely be clouded by persistent nausea. We are indeed comparing the two combinations but ondansetron (Zofran) and diphenhydramine (Benadryl) are simply adjuncts.

#### 5. Subjects:

Male and female DoD beneficiaries aged 18-65 years who present to the Emergency Department (ED) with complaint of a headache will be recruited at the Mike O'Callaghan Federal Medical Center (MOFMC). No special populations (e.g., pregnant women, children, prisoners, detainees) will be recruited.

#### 6. Inclusion/exclusion criteria:

# **Inclusion Criteria**

- Age 18 to 65 years who present to the ED with complaint of a headache
- Temperature < 100.4° F
- Diastolic blood pressure < 104 mm Hg

- Normal neurologic exam and normal mental status

#### **Exclusion Criteria**

- Pregnant or breastfeeding
- Meningeal signs are present

- Acute angle closure glaucoma is suspected
- Head trauma within the previous two weeks
- Lumbar puncture within the previous two weeks
- Thunderclap (rapid) onset of the headache
- Weight more than 150 kg or less than 40 kg
- Known allergy to diphenhydramine (Benadryl)
- Known allergy to ondansetron. (Zofran)
- Known allergy to compazine
- Known allergy to Ketamine
- History of schizophrenia or bipolar disorder
- History of intracranial hypertension
- Is a prisoner
- Patient declined informed consent
- Non-English speaking patient
- Attending provider excludes patient
- Elderly patients with dementia
- Patients with severe headaches that diminish their decision making capability will not be able to participate.

# 7. Number of Subjects:

TOTAL NUMBER OF SUBJECTS (nation-wide/study-wide): 70

#### 8. Use of an Investigational New Drug:

Ketamine and compazine are both drugs approved by the Food and Drug Administration. Ketamine is used as an analgesic during diagnostic and surgical procedures and compazine for the relief of nausea. In this protocol, they are both being used for a non-FDA approved indication (headache). Ketamine is frequently used for analgesia in the low doses described in this protocol. We are not intending to change marketing, FDA approved indications, or change dosing requirements. Compazine has been studied in multiple cases for migraine though is not specifically labeled for analgesia or migraine treatment, but is for nausea (an often experienced component of migraine).

9. Use of an Investigational Device: N/A

10. Use of a Placebo: N/A

# 3. Research Plan:

#### 3.1. Purpose:

This will be a prospective, double-blinded, randomized controlled trial on a convenience sample of patients presenting to the Emergency Department (ED) with a chief complaint of headache.

# 3.2. Hypotheses, Research Questions or Objectives:

We will determine the difference in pain scores between the compazine and Ketamine groups, as measured by a 25-mm difference between the groups mean on the visual analogue scale (VAS) at 60 min.

# 3.3. Significance:

Approximately 2.8% of ED visits are related to headache with a large percentage due to migraines making this diagnosis and its management a daily challenge for EM physicians [1]. The range of medications used to treat migraines has expanded without a clear first line therapy and each class has its own limitations not limited to medication interactions, cardiac effects, and short administration windows. Finding a safe and effective alternative to standard therapy could potentially save costs, reduce repeat visits, and more importantly alleviate this common and painful condition.

#### 3.4. Military Relevance:

Military Treatment Facilities often treat this condition. Low Dose Ketamine (LDK) has been extensively studied for battlefield analgesia and thus is often available to the downrange provider whereas phenothiazines such as compazine or alternative migraine treatments may not be. There is the potential for returning patients to function earlier, improving readiness and reducing the reliance on quarters for this condition's management.

### 3.5. Background and Review of Literature:

In the emergency department (ED), one of the most common chief complaints is headache [1]. A number of prior studies have demonstrated the efficacy of a variety of medications for migraines and other benign headaches [2]. Some of the options for treating these types of headaches include dopamine antagonists, opioids, non-steroid anti-inflammatory drugs (NSAIDs), triptans, anti-epileptics, and ergot derivatives [2]. Amongst the available options, dopamine antagonists appear to be the most effective, with multiple studies demonstrating their superiority over opioids [3], NSAIDs [4], triptans [5], and anti-epileptics [6]. The dopamine antagonist that we use most frequently, and the one that has the most evidence to support its use for benign headaches, is compazine [5,6,7,8,9,10]. Although some data suggest that droperidol may be even more effective than compazine [11], the current national shortage limits its use.

Despite the general effectiveness of dopamine antagonists and the variety of options for benign headache treatment, many patients who present to the ED still have headaches 24 hours after treatment. In one study by Friedman, 31% of patients still had moderate to severe headaches 24 hours after discharge [12]. Often we resort to opiates in refractory headaches despite evidence to suggest that opiates increase both length of stay and bounce backs [13].

Ketamine is an N-Methyl-D-aspartate (NMDA) receptor antagonist that has both analgesic and dissociative properties [14]. Previous studies have demonstrated the effectiveness of Ketamine for post-operative pain [15,16], pain in burn patients [17], and chronic pain [18]. New studies have also shown Ketamine to be useful for acute pain in the ED by both the intranasal [19] and intravenous routes [20]. To our knowledge, there are no prospective studies that evaluate the effectiveness of Ketamine for the treatment of benign headaches in the ED.

Diphenhydramine (Benadryl) and Ondansetron are being given in this study to manage the side effects from the comparison medications (Compazine –akathisia, ketamine –nausea). Diphenhydramine (Benadryl) itself doesn't add any benefit for migraines. [21] Ondansetron (Zofran) significantly reduces ketamine associated emesis [22]. Since nausea is common in migraines (73%) [23], and ketamine does not itself correct this it's logical and ethical to add this as an adjunct for ketamine. If we didn't add it to the regiment our satisfaction data would likely be clouded by persistent nausea. We are indeed comparing the two combinations but ondansetron (Zofran) and diphenhydramine (Benadryl) are simply adjuncts.

# 3.6. Research Design and Methods:

Male and female DoD beneficiaries aged 18-65 years who present to the ED with complaint of a headache will be offered an opportunity to participate in the study at the Mike O'Callaghan Federal Medical Center (MOFMC). Research subjects will be recruited when both research staff and a trained Pharmacist attached to this study are available. The PI or AI will not recruit their own patients to prevent any misconception of coercion or undue influence.

# **Screening Visit:**

- Obtain signed Informed Consent Document and HIPAA Authorization (research-driven).
- Record: Date of birth, age, phone number, gender, race, ethnicity, social security number, name of standard of care rescue medications (over-the-counter and prescription), current email address (to be used for scheduling only), height (in inches), weight (in pounds), history of traumatic brain injury, concussion, or any mild to severe head trauma, medication use. (research only)
- Review past medical history in Armed Forces Health Longitudinal Technology Application (AHLTA) or ESSENTRIS to verify the inclusion/exclusion criteria.
- Women of childbearing potential will have a serum pregnancy test (5-10 milliliters, approximately 1-2 teaspoons of blood) or urine pregnancy test (10 drops or less than 1 milliliter of urine) (research-driven).

#### Visit 1:

- Heart rate
- Blood pressure
- Headache severity via 100-mm VAS.
- Nausea severity via 100-mm VAS.
- Vomiting severity via 100-mm VAS.
- Anxiety severity via 100-mm VAS.
- Restlessness severity via 100-mm VAS.
- Record type and amount of rescue medications (over-the-counter and prescription) use in the past 7 days.
   (research only)
- Subjects will be randomized by the pharmacy. We will use a random-number generator and use blocking to ensure roughly equal sample sizes. Both subjects and investigators will be blinded to the study group assignments. Subjects will be randomized by the pharmacy into one of two groups (research-driven):
  - Group 1: Standard treatment arm (compazine 10 mg IV along with diphenhydramine(Benadryl) 25 mg
     IV)
  - Group 2: Research arm (Ketamine 0.3 mg/kg along with ondansetron (Zofran) 4 mg IV)

#### 15 minutes post treatment:

- Heart rate
- Blood pressure
- Headache severity via 100-mm VAS.
- Nausea severity via 100-mm VAS.
- Vomiting severity via 100-mm VAS.
- Anxiety severity via 100-mm VAS.

Restlessness severity via 100-mm VAS.

#### 30 minutes post treatment:

- Heart rate
- Blood pressure
- Headache severity via 100-mm VAS.
- Nausea severity via 100-mm VAS.
- Vomiting severity via 100-mm VAS.
- Anxiety severity via 100-mm VAS.
- Restlessness severity via 100-mm VAS.

#### 45 minutes post treatment:

- Heart rate
- Blood pressure
- Headache severity via 100-mm VAS.
- Nausea severity via 100-mm VAS.
- Vomiting severity via 100-mm VAS.
- Anxiety severity via 100-mm VAS.
- Restlessness severity via 100-mm VAS.

#### 60 minutes post treatment:

- Heart rate
- Blood pressure
- Headache severity via 100-mm VAS.
- Nausea severity via 100-mm VAS.
- Vomiting severity via 100-mm VAS.
- Anxiety severity via 100-mm VAS.
- Restlessness severity via 100-mm VAS.

Ketamine or compazine) and "randomized add-on medication" (for the ondansetron (Zofran) or diphenhydramine (Benadryl)). It is common practice to use the combination of compazine and diphenhydramine (Benadryl) or ketamine and ondansetron (Zofran). If the patient receives a rescue medication, he or she will definitely NOT be withdrawn from the study. The need for rescue medication is a secondary outcome of the study. We will still analyze groups based upon their original randomization and the intention to treat principle. Rescue medications do not bias the study results, and they have been part of every headache treatment study I have ever read. The data from the first 30-minutes will be maintained as research data, and this is important data for the study.

**Safety:** After 30 minutes, the treating provider will be permitted to administer any medication they would like for further treatment. Only if there is an untoward event that requires the treating provider to know which medication was administered will the pharmacist unblind the randomization for that individual patient.

# 3.6.1. Interventions, Observations, or Data Sought:

The primary outcome measure will be the difference in pain scores between the compazine and Ketamine groups, measured as the absolute difference between the means at 60 min. Secondarily, we will measure the difference between the rates of decline in pain scores, rate of admission, nausea scores, rate of vomiting, rate of development of akathisia, heart rate and blood pressure changes, headache resolution with telephone follow up, and patient satisfaction.

#### 3.6.2. Data Collection and Processing:

Data will be collected and recorded in a spreadsheet. At the conclusion of the study, all personally identifying information will be removed prior to analysis. De-identified data will be shared with research staff at University Medical Center of Southern Nevada at the conclusion of the study. A Cooperative Research and Development Agreement (CRADA) for the data sharing is pending.

#### 3.6.3. Setting:

Male and female DoD beneficiaries aged 18-65 years will be recruited at the Mike O'Callaghan Federal Medical Center (MOFMC). No special populations (e.g., pregnant women, children, military basic trainees, prisoners, detainees) will be recruited.

# 3.6.4. Date(s):

April 2016-April 2019

#### 3.6.5. Source of Research Material:

Source of Research Material per Participant	# Routine	# Research	# Total
(Procedures)	Care	Driven	Procedures
Medical Record Review	0	1	1
Serum or urine pregnancy test	0	1	1
Heart rate	0	5	5
Blood pressure	0	5	5
Headache severity via 100-mm VAS	0	5	5
Nausea severity via 100-mm VAS	0	5	5
Vomiting severity via 100-mm VAS	0	5	5
Anxiety severity via 100-mm VAS	0	5	5
Restlessness severity via 100-mm VAS	0	5	5

#### 3.6.6. Subjects:

Male and female DoD beneficiaries aged 18-65 years who present to the ED with complaint of a headache will be recruited at the Mike O'Callaghan Federal Medical Center (MOFMC). No special populations (e.g., pregnant women, children, prisoners, detainees) will be recruited.

#### 3.6.7. Inclusion/Exclusion Criteria:

#### Inclusion Criteria

- Age 18 to 65 years who present to the ED with complaint of a headache
- Temperature < 100.4° F
- Diastolic blood pressure < 104 mm Hg
- Normal neurologic exam and normal mental status

# **Exclusion Criteria**

- Pregnant or breastfeeding
- Meningeal signs are present
- Acute angle closure glaucoma is suspected
- Head trauma within the previous two weeks
- Lumbar puncture within the previous two weeks
- Thunderclap (rapid) onset of the headache
- Weight more than 150 kg or less than 40 kg
- Known allergy to diphenhydramine (Benadryl)
- Known allergy to ondansetron. (Zofran)
- Known allergy to compazine
- Known allergy to Ketamine
- History of schizophrenia or bipolar disorder
- History of intracranial hypertension
- Is a prisoner
- Patient declined informed consent
- Non-English speaking patient
- Attending provider excludes patient
- Elderly patients with dementia
- Patients with severe headaches that diminish their decision making capability will not be able to participate.

# 3.6.8. Instrumentation: N/A

# 4.0. Human Subject Protection:

#### 4.1. Recruitment:

All potentially eligible patients, presenting to the ED with a chief complaint of headache, will be offered an opportunity to participate. Some patients may be patients of the PI or AI, however, they will have the study staff recruit their patients to prevent any misconception of coercion or undue influence. When a potential subject is identified by the treating physician, the Research Staff will be contacted to speak with the patient directly. Research subjects will be recruited when both research staff and a trained Pharmacist attached to this study are available. Research subjects will be offered the opportunity to participate when they present to the Emergency Department either when they check-in, are waiting in the waiting area, or being triaged by Emergency Department personnel. Emergency Department staff will ask the patient if they are willing to speak with the research staff and, if they agree, then the research staff will be contacted to come discuss the study with the potential participant. An advertisement will be placed in the Emergency Department.

#### 4.2. Consent Processes:

Informed Consent and HIPAA authorization will be sought in advance of any study-related procedures from each prospective subject and appropriately documented in accordance with 32 CFR 219.117. Potential candidates will be notified about the study either through posted advertisements or by their care provider and will be given the opportunity to consent by one of the referred study coordinators. The study coordinator will provide a written copy of the Informed Consent Document (ICD). The subject may decline to consent without prejudice. At the subjects' discretion, they may take the ICD home to discuss further prior to making a decision

and if they decide they are interested in participating, they can contact the research department the next time they present to the Emergency Department with a headache. If the subject consents, a copy of the ICD will be given to the subject. No vulnerable populations are included in this research study. Subjects who cannot provide Informed Consent will not be allowed to participate. No Legally Authorized Representatives (LAR) will be utilized. Patients who experience severe headaches that are unable to provide informed consent will not be able to participate.

# 4.3 Participation Compensation:

Subjects will not be paid for participation in this study.

#### 4.4. Assent Process: N/A

# 4.5. Benefits:

There may be no direct benefits to the subjects for participating in this study. Personal benefits include intended reduction in headache symptoms and the satisfaction that the patient may be assisting investigators in determining a more effective headache treatment.

**4.6. Risks:** There is a risk of inadvertent breach of confidentiality. The potential risks to participate in this study are minimal and include:

DRUG NAME	LIKELY and not	LESS LIKELY and not serious	RARE and serious
	serious		
COMPAZINE (PROCHLORPERAZINE)	Drowsiness	Blurred vision Xerostomia (dry mouth) Congestion Nausea Akasthisia (restlessness) Tardive dyskinesia (involuntary movements) Electrocardiogram (ECG) changes Tachycardia (rapid heartbeat) Constipation Urinary retention Allergic reaction	Neuroleptic Malignant Syndrome (NMS) Blood dyscrasia (disease) Hypotension (low blood pressure)
KETAMINE	Drowsiness	Sialorrhea (excessive drooling) Nausea/vomiting Elevation in blood pressure or heart rate Nystagmus/diplopia (uncontrolled eye movements) Fasciculations (muscle twitch) Hallucinations Bradycardia (slow heart rate) Hypotension (Low blood pressure) Arrythmias (abnormal heart rhythm) Respiratory depression Cystitis (bladder inflammation) Pain at injection site	None
ONDANSETRON (ZOFRAN)	None	Headache Constipation Diarrhea	Serotonin syndrome Torsade de pointes

		Dizziness Drowsiness Fatigue Weakness QT interval prolongation Abdominal pain Dry mouth	Stevens-Johnson Syndrome Toxic Epidermal Necrolysis Hypersensitivity ECG changes
		Elevated liver enzymes	
DIPHENHYDRAMINE (BENADRYL)	Drowsiness Dry mouth	Dizziness Headache Blurred vision Tinnitus Hypotension Palpitations Anorexia Dry mouth Constipation Nausea Dysuria (Painful or difficult urination) Urinary retention or increase in frequency	None

#### 4.7. Costs: N/A

#### 4.8. Safeguards for Protecting Information:

The research consents will be stored in a locked cabinet in a locked room. Medical records will be annotated with ICD-10 code Zoo.6 to reflect the subject's participation in a research study. All research data including patient demographics will be kept in an electronic database, which will be encrypted, double password protected and the access will be restricted. The research data will be coded and any links to identifiable data will be destroyed as soon as the Final Report Approval has been obtained from the IRB. Only the pharmacist and the Research Coordinator will have access to the randomization records and will not reveal the randomization until the end of the study or in the event of a research related adverse event. The anonymized research data will not be utilized for further research activity beyond the protocol stipulations without additional IRB approval. De-identified data will be shared with research staff at the University Medical Center of Southern Nevada at the conclusion of the study. A Cooperative Research and Development Agreement (CRADA) for the data sharing is pending.

# 4.9. Safeguards for Protecting Subjects:

The principal investigator will be responsible for the protocol safety monitoring. The PI will make study documents (e.g., consent forms, data pulls) and pertinent hospital or clinical records readily available for inspection by the local IRB and oversight staff for confirmation of the study data.

#### 4.9.1. Minimizing Risks:

Subjects will have access to study personnel should they have any issues. If there are any issues, they will be immediately reported to one of the Investigators and an applicable medical evaluation will be initiated.

# 4.9.2. Vulnerable Populations: N/A

#### 4.9.3. Clinical Care:

All subjects will receive standard of care regardless of inclusion into this study. If at any time a subject experiences any injury or adverse effects, appropriate clinical care will be given or subject will be referred to appropriate provider.

# 4.9.4. Injury Compensation: N/A

# 4.9.5. Data Safety Monitoring:

The principal investigator will be responsible for the protocol safety monitoring. The PI will make study documents (e.g., consent forms, data pulls) and pertinent hospital or clinical records readily available for inspection by the local IRB and over sight staff for confirmation of the study data.

#### 5.0. Alternatives:

The alternative is to receive standard of care and not to participate in this study.

#### 6.o. Data Analysis:

A couple prior studies have used a 25-mm difference in mean VAS score reduction between groups to show a clinical benefit [6,9]. We define adequate pain relief as an absolute decrease in the mean VAS score of 25 mm [24, 25, 26, 27].

#### 6.1. Outcome Measures:

The primary outcome measure will be the difference in pain scores between the compazine and Ketamine groups, measured as the absolute difference between the means at 60 min. Secondarily, we will measure the difference between the rates of decline in pain scores, rate of admission, nausea scores, rate of vomiting, rate of development of akathisia, heart rate and blood pressure changes, headache resolution with telephone follow up, and patient satisfaction.

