#### 6.2. Sample size estimation/power analysis:

Thirty-two patients will be needed in each group to find a 25-mm difference between the group means on the VAS at 60 min, with a power of 0.80 and an alpha of 0.05. We will aim for 35 patients per group to account for about a 10% dropout rate

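### The primary 60-minute VAS comparison makes no use of the pre-dose VAS, giving up precision and leaving the result exposed to chance baseline imbalance

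*Combined protocol and SAP*

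**What the plan says.** Sections 3.6.1 and 6.1 both define the primary outcome as the difference in pain scores between the two arms, "measured as the absolute difference between the means at 60 min". The objective in 3.2 agrees ("as measured by a 25-mm difference between the groups mean on the visual analogue scale (VAS) at 60 min"), and section 6.2 sizes the trial on the same contrast: 32 per arm "to find a 25-mm difference between the group means on the VAS at 60 min", with power 0.80 and alpha 0.05, raised to 35 per arm for dropout.

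The pre-dose score is available. The Visit 1 list in section 3.6 includes "Headache severity via 100-mm VAS", and the table in 3.6.5 counts five headache VAS scores per participant, which fits Visit 1 plus 15, 30, 45 and 60 minutes.

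Section 6.3 uses presenting severity once, in a chi-square test of whether the arms are similar. It then says that the individual VAS measurements will be compared by repeated measures ANOVA. It does not say whether Visit 1 is one of the time levels, which effect tests the primary outcome, or whether there is a covariate.

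Section 6.0 takes the 25-mm yardstick from earlier studies that used a "25-mm difference in mean VAS score reduction between groups".

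**The concern.** Nothing in the design limits chance differences in presenting pain, and nothing in the stated primary contrast absorbs them. The clinical entry condition is "Age 18 to 65 years who present to the ED with complaint of a headache", with no minimum or maximum pain score, so pre-dose scores may be widely spread. Randomisation uses blocks to keep arm sizes roughly equal, and no stratification by severity is stated. With about 64 completers, one arm can by luck start with worse headaches, and part of that difference will carry into the 60-minute means.

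At stake are the width of the interval around the primary estimate and how the result can be defended. If the similarity test in 6.3 shows an imbalance, the plan offers no pre-specified adjusted result, and any adjustment chosen then would be post hoc.

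**Working it through.** **Inputs from the documents.** 32 per arm, 25 mm, power 0.80, alpha 0.05 (section 6.2). Sidedness is not stated; two-sided is assumed.

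**Inputs not in the documents.** The SD at 60 minutes, the pre-dose SD (SDb) and the correlation r between pre-dose and 60-minute VAS. The first is solved from the stated sample size. The others are assumed: r from 0.2 to 0.5, SDb from 20 to 25 mm.

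**Step 1: the plan's own figure.** Without an SD, 32 per arm cannot be reproduced directly. Solving the two-sided two-sample t-test for the SD gives 35.1 mm (35.7 mm by the normal approximation; 39.8 mm if the test were one-sided).

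- SE of the raw difference = 35.1 × √(2/32) = 35.1 × 0.25 = 8.8 mm
- 95% CI half-width = 2.00 × 8.8 = 17.6 mm
- Power at 25 mm = 0.80, by construction

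**Step 2: adjust for the pre-dose score.** Residual SD = 35.1 × √(1 − r²), and SE = residual SD × 0.25. Half-widths use unrounded SEs.

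| r | SE (mm) | 95% half-width (mm) | Power at 25 mm | n per arm for 0.80 |
|---|---|---|---|---|
| no adjustment | 8.8 | 17.6 | 0.80 | 32 |
| 0.2 | 8.6 | 17.2 | 0.82 | 31 |
| 0.3 | 8.4 | 16.8 | 0.84 | 30 |
| 0.5 | 7.6 | 15.2 | 0.90 | 25 |

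**Step 3: effect of chance imbalance.** The difference in mean pre-dose VAS has SD = SDb × 0.25. The slope of 60-minute on pre-dose VAS is r × 35.1/SDb. A 1-SD imbalance therefore shifts the expected raw contrast by r × 35.1 × 0.25 = 8.8r mm, whatever SDb is: 1.8 mm at r = 0.2 and 4.4 mm at r = 0.5, or about 2 to 4 mm.

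Larger imbalances are uncommon. With SDb = 20 mm the imbalance SD is 5 mm, and the arms differ by more than 10 mm in 4.6% of such trials; with SDb = 25 mm the figures are 6.25 mm and 11.0%. At r = 0.3 to 0.5, a 10-mm imbalance would shift the contrast by 5.3 to 8.8 mm in the first case and by 4.2 to 7.0 mm in the second.

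**Step 4: would a plain change score do instead?** With equal SDs at both times, its SD is 35.1 × √(2(1 − r)). Power at 32 per arm is 0.60 at r = 0.2, 0.66 at r = 0.3 and 0.80 at r = 0.5. Below r = 0.5 it does worse than the raw 60-minute comparison. ANCOVA carries no such penalty.

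**The case against.** The case for leaving the plan alone is substantial. Randomisation makes the unadjusted contrast unbiased. Its SE of 8.8 mm already includes variation from chance baseline differences, so type I error and interval coverage hold, and the trial is powered on exactly this contrast. All of that stands. The argument for adjustment is about efficiency.

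A reader might infer that the 25-mm benchmark is misapplied, because section 6.0 describes it as a difference in VAS reduction (and says "We define adequate pain relief as an absolute decrease in the mean VAS score of 25 mm") while the outcome is a 60-minute level. The documents do not support that. Under randomisation the expected pre-dose means are equal, so the expected difference at 60 minutes equals the expected difference in reduction. The wording differs; the target does not.

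A reader might also infer that the analysis as a whole disregards the pre-dose score. That is not shown either. With five VAS scores per participant, Visit 1 may well be a level of the repeated measures ANOVA, and its group-by-time term would then use it. But section 6.3 does not say so, and that term is not the 60-minute contrast defined in 6.1. The ambiguity is a reason to specify the model and does not answer the point.

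Finally, the gain depends on a correlation that the documents do not give. At r = 0.2 it is modest: about 0.35 mm of half-width and under two percentage points of power.

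**Conclusion.** The point holds as a matter of precision and robustness. The unadjusted 60-minute comparison is valid, but it sets aside a prognostic measurement that every participant provides, and section 6.3 names no model that puts it into the primary contrast.

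For r between 0.2 and 0.5, adjustment takes 0.4 to 2.4 mm off a 17.6-mm half-width and adds about 2 to 10 percentage points of power at 25 mm. This rests on a two-sided test, a 60-minute SD of about 35 mm implied by the sample size, and the assumed r. If r were zero there would be no gain, and the cost would be one degree of freedom.

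It would be too strong to call the planned contrast biased, or to treat a shift of 4 to 9 mm as typical. A shift of that size goes with a 10-mm baseline imbalance, which under the assumed pre-dose SDs is reached or exceeded in only about 5 to 11% of such trials.

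**What to change.** In 3.6.1, 6.1 and 6.3, state that the primary analysis is the between-group difference in mean headache VAS at 60 minutes, with its 95% confidence interval, from a linear model (ANCOVA) with treatment and the Visit 1 headache VAS as covariate. Report the unadjusted difference beside it. Keep the repeated measures analysis for the time course, and say in 6.3 that it is not the test of the primary outcome.

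Do not substitute a plain change score, for the reason in step 4 of the working. The ANCOVA estimate at 60 minutes is numerically the same as the baseline-adjusted difference in reduction, so it can be read directly against the yardstick in 6.0.

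The objective in 3.2 and the sample size in 6.2 can stand: 32 per arm was set without adjustment, so it is conservative for the adjusted analysis if r is appreciably above zero. The cost is a sentence or two in three sections and one degree of freedom, with no added patients, visits or measurements. The change should be fixed before unblinding.
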